The total duration of study participation for each subject only participating in the placebo-controlled period of the study will be up to approximately 102 weeks, including a series of Screening visits within 8 weeks before administration of the first dose, a 76-week placebo-controlled treatment period, and a safety follow-up (FU) period of approximately 18 weeks after the final dose. The total duration of study participation for each subject participating in the placebo-controlled period and the LTE period will vary and be up to approximately 362 weeks, including a series of Screening visits within 8 weeks before administration of the first dose, a 76-week placebo-controlled treatment period, a 4-week FU period, a 256-week aducanumab dose-blind treatment period, and a safety FU period of approximately 18 weeks after the final dose.

Investigators, study site staff (except for the designated unblinded pharmacist/technician), and study subjects will be blinded to the subjects' randomized treatment assignment for the placebo-controlled period. During the LTE period, investigators and subjects will remain blinded to the treatment assignment in the placebo-controlled period and the aducanumab dose for the LTE period.

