4 STATISTICAL ANALYSIS METHODS

4.1 General Considerations

This statistical analysis plan (SAP) only covers the analyses for the primary, secondary and tertiary objectives for the placebo-controlled portion of the study. Hereafter, the placebo-controlled portion of the study will be referred to as “the study” in the rest of this SAP (e.g.,

CONFIDENTIAL

The information contained herein may not be used, disclosed, or published without the written consent of Biogen MA Inc.

	Statistical Analysis Plan Placebo-Controlled Period	Final V1.0
---	---	-------------------

completion of the study means completion of the placebo-controlled portion). A separate SAP will be prepared for the analyses of the LTE period and integrated analyses across both portions of the study. The analyses of additional exploratory endpoints will be documented separately.

Summary tables will be presented using descriptive summary statistics. For continuous variables, summary statistics will generally include: number of subjects with data, mean, standard deviation, median, 25% percentile, 75% percentile, minimum and maximum. For categorical variables, this will generally include: number of subjects randomized or dosed, number with data, and the percent of those with data in each category.

There are two types of analysis displays for tables: by treatment group (analysis display A in Appendix 6.1) and by treatment group stratified by ApoE status (analysis display B in Appendix 6.1; here ApoE status refers to the status recorded in IXRS [see Table 1 for correspondence between treatment groups and treatment groups stratified by ApoE status]). The analysis display for each analysis will be defined in each section. All the listings will be presented by treatment group stratified by ApoE status, unless otherwise specified.

Unless otherwise specified, baseline value is defined as the most recent non-missing measurement collected prior to the first dose. Change from baseline will be defined as post-baseline value minus baseline value.

Unless stated otherwise, all statistical tests will be 2-sided with statistical significance level of 0.05.

The statistical software, SAS® will be used for all summaries and analyses.

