4.1.1 Analysis Population

- Intent-to-treat (ITT) population:
The Intent-to-treat population is defined as all randomized subjects who received at least one dose of study treatment (aducanumab or placebo).
- Per-protocol (PP) population:
The per-protocol population is defined as all subjects in the ITT population and also
 - had no violations of the following inclusion criteria:
 - Must have at least 6 years of education or work experience to exclude mental deficits other than MCI or mild AD;
 - Must have a positive amyloid PET scan;
 - Must have:
 - A CDR-Global Score of 0.5;
 - A Repeatable Battery for Assessment of Neuropsychological Status (RBANS) score of 85 or lower indicative of objective cognitive impairment (based upon the Delayed Memory Index score);
 - An MMSE score between 24 and 30 (inclusive).
 - had at least 14 infusions.
 - did not make any change to concomitant AD symptomatic medications during the study.

CONFIDENTIAL

The information contained herein may not be used, disclosed, or published without the written consent of Biogen MA Inc.

- **¹⁸F-florbetapir amyloid PET analysis population:**
The ¹⁸F-florbetapir amyloid PET analysis population is defined as all randomized subjects who received at least one dose of study treatment (aducanumab or placebo), used ¹⁸F-florbetapir ligand for amyloid PET scan, and had an evaluable baseline amyloid PET SUVR value for the composite region-of-interest using cerebellum as the reference region.
- **¹⁸F-flutemetamol amyloid PET analysis population (applicable only to Japan):**
The ¹⁸F-flutemetamol amyloid PET analysis population is defined as all randomized subjects who received at least one dose of study treatment (aducanumab or placebo), used ¹⁸F-flutemetamol ligand for amyloid PET scan, and had an evaluable baseline amyloid PET SUVR value for the composite region-of-interest using cerebellum as the reference region.
- **Safety population:**
The safety population is defined as all randomized subjects who received at least one dose of study treatment (aducanumab or placebo). It is the same population as the ITT population.
- **Safety MRI population:**
The safety MRI population is defined as all randomized subjects who received at least one dose of study treatment (aducanumab or placebo) and had at least one post-baseline MRI assessment.
- **PK analysis population:**

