* Analysis excludes data collected after the following intercurrent events: (1) premature discontinuation of the study treatment and (2) any change to concomitant AD symptomatic medications during the study. All other analyses will include data collected after intercurrent events [ICH E9 (R1) Addendum 2017].

Visit windows for mapping efficacy endpoint

For efficacy data that are summarized or analyzed by visit, data collected on all scheduled visits and all unscheduled visits will be mapped to an appropriate analysis visit using the windowing scheme shown in Table 3. If there are 2 or more assessments available in the same analysis window for a subject, the assessment that is closest to the target visit day will be used for analysis. If there are 2 or more assessments in the same analysis window with the same distance from the target visit day, the later assessment will be used.

Table 3. Visit Windows for Efficacy Endpoints

Analysis visit	Target visit day	Analysis visit window
Baseline	1	Most recent non-missing pre-dose value
Week 26	183	[92, 266]
Week 50	351	[267, 448]
Week 78	547	[449, the end day of the placebo-controlled period *]
* The end day of the placebo-controlled period is the last day before the first infusion in LTE for subjects who enter LTE, and is the last day in study for subjects who do not enter LTE.		

Handling of missing items for scales

If any of the individual items for the primary and secondary endpoints is missing, the total score of the corresponding endpoint will be imputed by prorating the observed scores [van Ginkel 2010].

For ADAS-Cog13, if 3 or fewer of 13 items (<25%) are missing, the total score will be imputed by the following algorithm: Total score = total score from the completed items * [maximum total score (=85) / maximum total score for the completed items]. The imputed number will be rounded up to the nearest integer. If more than 3 items are missing, the total score of ADAS-Cog 13 at that visit will be considered missing.

For ADCS-ADL-MCI, if 4 or fewer of 18 items (<25%) are missing, the total score will be imputed by a similar algorithm as that for ADAS-Cog 13. The imputed number will be

	Statistical Analysis Plan Placebo-Controlled Period	Final V1.0
---	---	-------------------

rounded up to the nearest integer. If more than 4 items are missing, the total score for ADCS-ADL-MCI at that visit will be considered missing.

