4.3.2.3 Supplementary analysis

4.3.2.3.1 Censoring after intercurrent events

The primary analysis (Section 4.3.2.1) will be repeated with the data censored after any of the following intercurrent events (if multiple events occur to the same subject, data after the earliest event will be censored):

- premature discontinuation of the study treatment;
- any change to concomitant AD symptomatic medications during the study.

The estimate of this analysis reflects the treatment effect of aducanumab if the drug is taken as directed.

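### The per-protocol rule on AD-medication changes has no Week 78 cut-off, so membership depends partly on events after the endpoint and on LTE entry

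*SAP*

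**What the plan says.** Section 4.1.1 sets three kinds of condition for the per-protocol population: no violation of certain entry criteria, a minimum exposure ("had at least 14 infusions"), and that the subject "did not make any change to concomitant AD symptomatic medications during the study". The last condition has no end date of its own.

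The end date comes from other sections:

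- Section 4.1: "Hereafter, the placebo-controlled portion of the study will be referred to as" the study. Its example is that "completion of the study means completion of the placebo-controlled portion".
- Section 4.3.1, footnote to Table 3: for LTE entrants the placebo-controlled period ends the day before the first LTE infusion. Otherwise its end "is the last day in study for subjects who do not enter LTE".
- Section 2.1: subjects who take part only in the placebo-controlled period have "a safety follow-up (FU) period of approximately 18 weeks after the final dose", and this time is counted in their total participation.

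Table 2 uses the per-protocol population for a supplementary MMRM of CDR-SB and of each secondary endpoint. Section 4.3.2.3.1 handles the same event in another way: "if multiple events occur to the same subject, data after the earliest event will be censored". A change after the Week 78 score therefore does nothing in that analysis.

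**The concern.** The per-protocol analysis estimates a difference at Week 78. For a subject assessed near the target day, a later medication change cannot have altered the score, but it may well follow from a poor one. Excluding the subject for it selects on the outcome. If the drug works and decline prompts medication changes, slightly more fast decliners leave placebo than an active arm, and the per-protocol difference is pulled toward zero.

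The rule also treats like subjects differently. Take two subjects with all 20 infusions and a Week 78 assessment, who both change a symptomatic drug at Week 85. The one who declined the LTE is removed. The one who entered it is kept, because for that subject the placebo-controlled portion is already over.

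**Working it through.** **Check of the plan's timeline (Section 2.1).** Placebo-controlled period only: 8 + 76 + 18 = 102 weeks, as stated. With the LTE: 8 + 76 + 4 + 256 + 18 = 362 weeks, also as stated. So the 18 weeks of follow-up are part of participation in the placebo-controlled period.

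**Length of the rule after the endpoint.** The Week 78 target is day 547 (Table 3).

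- Not entering the LTE: 20 doses every 4 weeks put the last dose at Week 4 × 19 = 76, day 1 + 7 × 76 = 533. Adding 18 × 7 = 126 days gives day 659 (Week 94). This is 659 − 547 = 112 days, or 16 weeks, after the target.
- Entering the LTE: the first LTE visit is Week 80 (LTE SAP, Section 3.5.3.2), day 1 + 7 × 80 = 561. The period ends on day 560, which is 560 − 547 = 13 days after the target.

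These dates are for subjects who follow the nominal schedule and receive all 20 doses.

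**How many subjects might be caught (assumed).** The SAP gives no rate of AD-medication change. Suppose a constant hazard with a proportion p changed by Week 78, so h = −ln(1 − p)/78 per week. Among subjects still unchanged at Week 78, the proportion changing in the next w weeks is 1 − exp(−h·w):

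| p by Week 78 (assumed) | Not entering LTE (w = 16) | LTE entrants (w = 13/7) |
|---|---|---|
| 5% | 1.0% | 0.1% |
| 10% | 2.1% | 0.3% |
| 20% | 4.5% | 0.5% |

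Suppose also that 10% to 30% of placebo subjects are followed past Week 78 without entering the LTE. They then contribute between 0.10 × 0.95 × 1.0% ≈ 0.1% and 0.30 × 0.80 × 4.5% ≈ 1.1% of placebo subjects. At the upper end, the entrants' 13 days add about 0.70 × 0.80 × 0.5% ≈ 0.3 points.

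**Effect on the difference.** Section 3 supplies the planning figures: placebo mean change 2, difference 0.5 (so active mean 1.5), SD 1.92. Let the probability of exclusion be 1/(1 + exp(−(a + b·x))), where x is the Week 78 change, b = ln(1.5) or ln(2), and a is set to give the chosen placebo exclusion. The difference in means among those retained, by numerical integration, is:

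| Placebo excluded after Week 78 (assumed) | Odds 1.5 per point | Odds 2 per point |
|---|---|---|
| 0.3% | 0.499 | 0.498 |
| 1.0% | 0.497 | 0.493 |

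In the last cell, the active arm loses 0.72% and the retained means are 1.975 and 1.482, a difference of 0.493. The shrinkage is 0.007/0.50 = 1.4%. Reaching 0.47 to 0.49 would need 3% to 5% of all placebo subjects to be excluded for changes after Week 78, and nothing in the SAP supports that.

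**The case against.** The best defence is that little depends on this. The per-protocol analysis is one of five supplementary analyses of CDR-SB and lies outside the multiplicity procedure (Section 4.3.1). The primary MMRM keeps all data after medication changes. Any bias would most likely run toward no difference, so it would not create a positive result. All of this stands, and it limits the weight of the point.

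Three further qualifications also stand:

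- LTE entrants have about 13 days of exposure to the rule after the target, so LTE entry changes the length of that exposure, not its existence.
- The Week 78 window runs to the end of the placebo-controlled period. For a subject whose only Week 78 assessment is late, a change in early follow-up can precede the score that is used.
- The rule has an effect only if medication changes are recorded throughout follow-up. That is likely, but the SAP leaves the visit schedule to the protocol.

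A reader might go further and object to removing whole subjects for any medication change, earlier changes included. Under the same model, excluding 10% to 20% of placebo subjects for the whole criterion would give 0.42 to 0.48. That figure does not measure the missing cut-off, because nearly all of those exclusions would come from changes before Week 78. Removing subjects for post-baseline conditions is also what a per-protocol population does, and the 14-infusion rule does the same. The SAP already plans the alternative of keeping data up to the change, in Sections 4.3.2.3.1 and 4.3.3.4.

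None of this supplies the missing end date.

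**Conclusion.** The point holds as a gap in the definition. By the SAP's own terms, the exclusion period runs about 16 weeks past the Week 78 target for subjects not entering the LTE and about 2 weeks for entrants. Per-protocol membership thus depends partly on events after the score and on LTE entry.

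The size is probably small: about 0.493 to 0.499 in place of 0.50. This rests on assumed placebo exclusion of 0.3% to 1%, assumed odds of 1.5 to 2 per CDR-SB point, and the planning means and SD. A higher rate of change after Week 78 would enlarge it, but the SAP gives no rate.

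The SAP does not support an inference that the primary result is biased, that LTE entrants escape the rule altogether after Week 78, or that the handling of earlier changes must be rewritten.

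**What to change.** In Section 4.1.1, count only AD symptomatic medication changes dated on or before the subject's Week 78 efficacy assessment, or on or before the last efficacy assessment if there is none at Week 78. Apply the same cut-off whether or not the subject enters the LTE. Tying it to the subject's own assessment date, not to day 547, also deals with late Week 78 assessments.

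Leave the handling of earlier changes as it is.

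The cost is one clause. Section 4.2.3 already plans to list start and stop dates of these drugs for subjects with a change, so no new data are needed. A few more subjects stay in the per-protocol set, and the primary analysis is unchanged.

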4.2 Background Characteristics

The summaries in this section will be based on the ITT population. Unless otherwise specified, summary tables will be presented by treatment group (analysis display A in Appendix 6.1) and by treatment group stratified by ApoE status (analysis display B in Appendix 6.1; here ApoE status refers to the status recorded in IXRS [see Table 1 for correspondence between treatment groups and treatment groups stratified by ApoE status]). All the listings will be presented by treatment group stratified by ApoE status, unless otherwise specified.

4.2.1 Accounting of Subject

Disposition of subjects will be summarized and the summary data will include number (%) of subjects randomized and dosed, number (%) of subjects who completed the treatment/study, and number (%) of subjects who discontinued treatment and/or withdrew from study. For subjects who discontinued treatment and/or withdrew from study, the reasons for discontinuation and/or withdrawal, and days on treatment and days on study will be summarized and listed. The number of subjects discontinuing treatment prior to each scheduled clinical efficacy assessment will be summarized (presented by treatment group), i.e., the number of subjects discontinuing treatment between Day 1 and Week 26, the number of subjects discontinuing treatment between Week 26 and Week 50 visit, etc. A similar summary will be done for subjects who withdrew from study (presented by treatment group). Time to treatment discontinuation and time to study withdrawal will be displayed by Kaplan-Meier plot (presented by treatment group).

Number of subjects in each analysis population will be summarized. Number of subjects dosed will be summarized by region, country and site. In addition, number of subjects who completed the treatment/study will be summarized by region and country (presented by treatment group).

The categorization of region is based not only on consideration of geography but also on type of health care system and access to health care in each country. This region category will be used in all analysis, including the demographics, the covariate in statistical models and subgroup analysis. The categories for regions will be:

- Region 1: United States (US);
- Region 2: European countries (including Belgium, Finland, France, Germany, Italy, Netherlands, Poland, Spain, Sweden and Switzerland), plus Canada;
- Region 3: Asia countries (including Japan).

4.2.2 Demographics and Baseline Characteristics

The demographic data including age, gender, ethnicity, race, height, weight, and body mass index (BMI) will be summarized. Age will also be categorized and presented using the following two groupings: <50, 50-60, 61-70, 71-80, 81-85, >85 years, and ≤ 64, 65-74, ≥ 75.

Summary of the baseline characteristics of AD includes laboratory ApoE ε4 status (carrier or non-carrier), baseline clinical stage (MCI due to AD or mild AD), baseline clinical assessment including RBANS delayed memory index, CDR global score, CDR-SB, CDR cognitive subscore, CDR functional subscore, MMSE, ADAS-Cog 13, ADCS-ADL-MCI, number of years of formal education, number of years since first AD symptom, number of years since diagnosis of AD, AD treatment use that was stopped prior to entering the study (yes or no) and AD symptomatic medication use at baseline (yes or no; see Section 4.2.3 for definition of AD symptomatic medication use at baseline). ApoE ε4 carrier will be further classified as homozygote and heterozygote. MMSE will also be categorized by the following subgroups: <24, 24-26, 27-30. Subject listings will be generated for demographics and baseline characteristics.

Medical history will be coded using the Medical Dictionary for Regulatory Activities (MedDRA). The number (%) of subjects with history (including both ongoing and not ongoing medical conditions) will be summarized by system organ class and preferred term. A listing of medical history will be generated.

Previous therapies for the treatment of AD stopped prior to entering the study, total duration of previous therapies and reason for stopping treatment will be summarized (presented by treatment group). A listing of previous therapies will also be generated.

4.2.3 Concomitant Medications and Non-Drug Therapies

All concomitant medications will be coded using the World Health Organization (WHO) medication dictionary. All concomitant non-drug therapies will be coded using the MedDRA dictionary. A concomitant medication/therapy will be defined as any therapy that was taken on or after the day of the first dose of study drug. This includes therapies that start prior to the initiation of the first dose if their use continues on or after the date of first dose. To define concomitant use for therapies with missing start or stop dates, the following additional criteria will be used:

- if both the start and stop dates of a therapy are missing, that therapy will be considered concomitant.
- if the start date of a therapy is missing and the stop date of that therapy fall on or after the date of the first dose, that therapy will be considered concomitant.
- if the start date of a therapy is prior to the date of the first dose and the stop date of that therapy is missing and the therapy is listed as continuing, that therapy will be considered concomitant, or
- if the start date of a therapy is prior to the date of the first dose and the stop date of that therapy is missing and the therapy is not listed as continuing, that therapy will be considered non-concomitant.

For a therapy with a partial start date, the year/month of the therapy date will be compared to that of the first dosing date to determine whether the therapy is concomitant.

The number (%) of subjects taking concomitant medication and non-drug therapies will be summarized. Non-drug therapies will be presented by treatment group. Concomitant medications and non-drug therapies will be listed.

AD symptomatic medications taken concomitantly at baseline are defined as AD symptomatic medications that were being taken at the time of the first dose, i.e., started prior to the first dose and continued until after the first dose. The number (%) of subjects taking AD symptomatic medications concomitantly at baseline will be summarized. In addition, number of subjects using Cholinesterase inhibitors only, Memantine only, or both at baseline will be summarized. Subjects who have any change in AD symptomatic medications after the initiation of study treatment will be summarized by the timing of change, i.e., the number of subjects changing between Day 1 and Week 26, the number of subjects changing between Week 26 and Week 50, etc. The summary for AD symptomatic medication use during study

	Statistical Analysis Plan Placebo-Controlled Period	Final V1.0
---	---	-------------------

will be presented by treatment group. The start and stop date of AD symptomatic medication will be listed for these subjects.

4.2.4 Protocol Deviations

Protocol deviations identified during site monitoring will be captured in a Protocol Deviation log and categorized as major or minor deviations based on Protocol Deviation Classification (see Appendix 6.2). The major protocol deviations will be summarized (presented by treatment group). Listings will be generated for the major and minor protocol deviations, respectively. A listing will be generated for subjects with incorrect stratification ApoE status, i.e., treatment stratification ApoE ϵ 4 status in IXRS different from the laboratory ApoE ϵ 4 status.

